4.5 Analysis of Secondary Objectives

No correction to the testing level amongst the secondary variables will be made as these are considered non definitive and hypothesis generating. All analyses will be conducted on the MITT population only.

4.5.1 Efficacy (Secondary)

4.5.1.1 Overall Gum Comfort Score at Weeks 1, 4 and 8

Change from baseline in overall gum comfort questionnaire scores at Weeks 1, 4 and 8 (overall mean score) will be evaluated using the same model as used for primary efficacy analysis on the MITT population (Table 14.2.2.1).

4.5.1.2 Gum Comfort Questionnaire Individual Questions Scores

Summary of Individual Gum Comfort question scores will be presented (n, missing, mean, SD, SE, median, minimum and maximum) at Weeks 1, 4, 8 and 12 in Table 14.2.3.1. Individual Gum Comfort question scores will be statistical analyzed using the same model as used for primary efficacy analyses in Table 14.2.3.2.

4.5.1.3 Mucosal Score Assessment (MSA)

The MSA will be made on the denture bearing tissues using the scale described by Henriksen et al and summarized in Table 9-3 of the Protocol. The MSA score at each assessment is measure on a scale of 1 (normal appearance) up to 4 (severe inflammation).

A summary table of descriptive statistics (n, missing, mean, SD, SE, median, minimum and maximum) of the observed and change from baseline MSA values will be presented at each week (Table 14.2.4.1) for subjects in the MITT population.

Wilcoxon rank sum test will be used to compare the between-product group medians of change from baseline MSA values at each week and the Wilcoxon signed-rank test will be used to compare the within-product group medians of change from baseline MSA values at each week for subjects in MITT population. P-values for both tests will be reported along with median change from baseline values. (Table 14.2.4.2)

All MSA responses and change from baseline scores will be listed (Listing 16.2.6.2).

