## 3 STUDY OBJECTIVES AND ENDPOINTS

**Table 3-1 Study Objectives and Endpoints**

Objectives	Endpoints
Primary	
To compare the ability of an experimental denture adhesive to provide self-perceived mucosal benefits compared to the use of no adhesive after 12 weeks of product use.	Change from baseline in mean scores of subject responses to the Gum Comfort questionnaire after 12 weeks (overall mean score).
Secondary	
To compare the ability of an experimental denture adhesive to provide self-perceived mucosal benefits compared to the use of no adhesive after 1, 4 and 8 weeks of product use.	Change from baseline in mean scores of subject responses to the Gum Comfort questionnaire after 1, 4 and 8 weeks (overall mean score).
To compare the ability of an experimental denture adhesive to provide self-perceived mucosal benefits compared to the use of no adhesive after 1, 4 and 8 and 12 weeks of product use.	Change from baseline in mean scores of subject responses to the individual questions on the Gum Comfort questionnaire after 1, 4, 8 and 12 weeks.

To compare the ability of an experimental denture adhesive to reduce denture-bearing mucosal irritation compared to the use of no adhesive after 1, 4, 8 and 12 weeks of product use.	Change from baseline in examiner-derived scores from the mucosal assessment after 1, 4, 8 and 12 weeks.
To compare the ability of an experimental denture adhesive to provide self-perceived oral-health related quality-of-life benefits compared to the use of no adhesive after 1, 4, 8 and 12 weeks of product use.	Change from baseline in mean scores of subject responses to the OHIP-Edent and GOHAI questionnaires after 1, 4, 8 and 12 weeks (overall mean scores and average domain scores).
To assess the sensory attributes of an experimental denture adhesive.	Mean scores of subject responses to the sensory questionnaire after 28 days.
Safety	
To assess the tolerability of an experimental denture adhesive.	Treatment emergent adverse events.

This study will be considered successful if a statistically significant difference between the mean scores from the Gum Comfort questionnaire is observed between subjects using the experimental denture adhesive compared to subjects using no adhesive in favour of the experimental adhesive after 12 weeks use.

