Assessment of oral mucosal health in the edentulous has been investigated by Tarbet (Tarbet et al, 1980) who demonstrated that the use of a denture fixative was associated with improvements in the oral-mucosal health of subjects. The scoring system used in this study for evaluation of the oral-mucosal health was perhaps not sufficiently discriminatory enough for accurate evaluation of these subjects who mostly scored zero on this scale. An alternative scoring index for oral mucosal health in the dentate/edentulous has been evaluated (the mucosal score (MS)) (Henriksen et al, 1999) although not yet used to investigate clinical interventions. MS would appear to be more sensitive than the Tarbet score system for evaluation of subjects who have mild/moderate mucosal conditions and will therefore be used in this study.

The Kapur-Olshan index is a composite score based upon stability and retention ratings for the maxillary and mandibular dentures (Kapur, 1967; Olshan et al, 1992). In this study, subjects presenting with a very low Kapur-Olshan score at Screening (< 3 for each denture [maxillary and/or mandibular]), defined as “Clinically Poor” (Olshan et al, 1992), will be excluded from this study since the study adhesive is not recommended for use with poor fitting dentures.

Subjects with temporomandibular joint disorders are excluded should the investigator believes that this could affect the subject’s participation, principally regarding the ability for the subject to adequately chew. Subjects who use or have ever used bisphosphonate medications are specifically excluded from this study owing to the enhanced risk of bisphosphonate-related osteochemonecrosis of the jaw that is associated with reduced tissue tolerance to function with removable prostheses (Saldanha et al, 2012).

A no adhesive negative control treatment has been chosen to provide a continual reference point to allow interpretation of the results, and is representative of a significant number of denture wearers who currently do not use an adhesive (Coates, 2000).

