### **12.2.6 Secondary Analyses**

Analysis of the same primary variable at 1, 4 and 8 weeks will be identical to that of the primary variable at 12 weeks.

Other Questionnaire data at each time of assessment, the OHIP-Edent and GOHAI (including any subscales of each) will be analyzed in a similar fashion to the primary variable.

A summary of the Product Sensory Questionnaire at 28 days will be provided for the adhesive wearing group.

A summary of the incidence of denture bearing tissue assessments at each time of assessment on a scale of 1-4 will be presented.

No correction to the testing level amongst the secondary variables will be made as these are considered non definitive and hypothesis generating.

Further details will be given in the Reporting and Analysis Plan which will be finalized prior to database lock.

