4.4.2.1 Statistical Hypothesis, Model, and Method of Analysis

Descriptive statistics (n, missing, mean, SD, SE, median, minimum and maximum) of the primary variable observed value will be provided ([Table 14.2.2.1](#)) at Baseline, Weeks 1, 4, 8 and 12, along with the change from baseline statistics at Weeks 1, 4, 8 and 12 by product group for the MITT population and ([Table 14.2.2.4](#)) for PP population.

Frequency distributions of the overall gum comfort score by product group will be provided displaying the complete range of responses from 0 – 20 at each week ([Table 14.2.2.2](#)) for MITT population.

The primary analysis is a comparison of the mean change from baseline in overall gum comfort score between Experimental Adhesive and No Adhesive at Week 12 for subjects eligible for the MITT population.

The null hypothesis for the primary endpoint is that the mean change from baseline in overall gum comfort score is equal between the 2 groups.

$$H_0: \mu_1 = \mu_2$$

The alternative hypothesis is that the mean change from baseline in overall gum comfort score is not equal between the 2 groups.

$$H_1: \mu_1 \neq \mu_2$$

The change from baseline in overall gum comfort score at Week 12 will be analysed using analysis of covariance (ANCOVA) with study product as a fixed effect and baseline overall gum comfort score as a covariate. Adjusted means and their SEs, 95% confidence intervals (CI), within treatment p-values for each product group will be displayed with product group difference, SE, 95% confidence interval of the difference and the between-treatment p-value in [Table 14.2.2.3](#) for MITT population and in [Table 14.2.2.5](#) for PP population. All statistical tests of hypotheses will be two-sided and will employ a level of significance of $\alpha = 0.05$.

This study will be considered successful if a statistically significant difference between the adjusted mean scores of the two product groups is observed to be in favor of the Experimental Adhesive.

The assumptions of the ANCOVA model i.e. normality of residual and equality of variances will be investigated. If the assumptions of the underlying model are violated, data transformations will be investigated and if suitable transformations cannot be found, an appropriate non-parametric test will be performed (e.g. Mann-Whitney U test).

All Gum Comfort Questionnaire responses with the overall and change from baseline scores will be listed ([Listing 16.2.6.1](#)).

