4.5.1.4 OHIP-Edent Questionnaire

This questionnaire comprises 19 questions grouped into 6 functional domains as provided in [Table 4-1](#). The questions have 5 possible responses ranging from 0 (Never) to 4 (Very Often) scale for all questions and thus a low score is more favorable and the overall score range is 0-76 where 0 is the best possible score.

Table 4-1 The Functional Domains of the OHIP-Edent Questionnaire

Domain	Questions	Score range
Functional limitations	1-3	0-12
Physical pain	4-7	0-16
Psychological discomfort	8-9	0-8
Physical disability	10-12	0-12
Psychological disability	13-14	0-8
Social disability	15-19	0-20

Summary tables of descriptive statistics (n, missing, mean, SD, SE, median, minimum and maximum) of the observed and change from baseline overall OHIP-Edent score will be presented ([Table 14.2.5.1](#)) at each week and for OHIP-Edent functional domain scores over time ([Table 14.2.5.3](#)) for subjects in the MITT population.

The change from baseline in overall OHIP-Edent score at Weeks 1, 4, 8 and 12 will be analyzed using ANCOVA with study product as a fixed effect and baseline overall OHIP-Edent score as a covariate. Adjusted means and their SEs, 95% CI, within treatment p-values for each product group will be displayed with product group difference, SE, 95% CI of the difference and the between-treatment p-value in ([Table 14.2.5.2](#)). All statistical tests of hypotheses will be two-sided and will employ a level of significance of $\alpha = 0.05$. Similar model will be used to analyze change from baseline OHIP-Edent functional domain scores at weeks 1, 4, 8 and 12 ([Table 14.2.5.4](#)).

As with the primary efficacy analysis, the model assumptions will be checked and suitable transformations or alternative non-parametric method will be performed if these are not met.

All OHIP-Edent responses for each question will be listed ([Listing 16.2.6.3](#)) by functional domain including the functional domain score, change from baseline domain score and overall OHIP-Edent observed and change from baseline values.

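### The between-arm test on MSA change does not adjust for baseline MSA, and the SAP text gives it no between-group estimate or confidence interval

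*SAP*

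**What the plan says.** Protocol Table 3-1 sets a between-arm objective at Weeks 1, 4, 8 and 12: "To compare the ability of an experimental denture adhesive to reduce denture-bearing mucosal irritation compared to the use of no adhesive". The MSA is a four-level score, from 1 (normal) to 4 (severe inflammation).

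SAP 4.5.1.3 plans three things for it:

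- Table 14.2.4.1: descriptive statistics by arm (including n, mean, SD, SE and median) of observed values and change.
- Between arms: "Wilcoxon rank sum test will be used to compare the between-product group medians of change from baseline MSA values at each week". A signed-rank test is added within each arm.
- Table 14.2.4.2: "P-values for both tests will be reported along with median change from baseline values".

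The questionnaires are handled differently. The primary Gum Comfort model (SAP 4.4.2.1) is ANCOVA "with study product as a fixed effect and baseline overall gum comfort score as a covariate". Gum Comfort at Weeks 1, 4 and 8 and its individual questions use the same model (4.5.1.1, 4.5.1.2). OHIP-Edent and GOHAI use ANCOVA with their own baselines (4.5.1.4, 4.5.1.5). The OHIP-Edent overall-score table reports "product group difference, SE, 95% CI of the difference and the between-treatment p-value"; the primary and GOHAI overall analyses report the same quantities.

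On the status of all secondary endpoints, SAP 4.5 says: "No correction to the testing level amongst the secondary variables will be made as these are considered non definitive and hypothesis generating".

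Protocol 12.2.6 plans less for this outcome: "A summary of the incidence of denture bearing tissue assessments at each time of assessment on a scale of 1-4 will be presented". I read this as the MSA, because the separate denture bearing tissue score is taken only at screening.

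**The concern.** Two features of the MSA plan sit badly with the scale.

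First, a subject who starts at 1 cannot improve. Subtracting baseline does not remove that floor: the unstratified test ranks such subjects together with subjects who had room to improve. Baseline MSA therefore carries information that the test does not use, although it is already collected.

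Second, change on a four-level score is heavily tied at 0. A rank sum test on such data is not a comparison of medians, and both medians can be 0 when the arms clearly differ. A p-value beside two zeros does not tell the reader how large the difference is or how well it is known.

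Subjects know their arm (Protocol 4.2) and complete every other efficacy measure themselves. The MSA is the only efficacy outcome from a blinded examiner. For a hypothesis-generating endpoint, the size of the difference and its CI are the main product.

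**Working it through.** **The plan's own figure.** There is no power figure for the MSA. The only one is 90% assurance for Gum Comfort with 57 evaluable per arm (SAP 1.4). Averaging two-sample power over SD ~ Normal(0.8, 0.0862), with 0.0862 read as an SD, gives 90.4% (noncentral t) to 90.9% (normal approximation), so it reproduces. It does not bear on the MSA; only the 57 per arm is carried forward.

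**Example 1: what the planned table could show.** Assumed counts, 57 per arm: adhesive 25 improved by one, 30 unchanged, 2 worse by one; no adhesive 10, 41, 6.

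- Tie groups: 35, 71 and 8 (N=114). Midranks: 18, 71 and 110.5.
- W = 25×18 + 30×71 + 2×110.5 = 2801. E = 57×115/2 = 3277.5.
- V = (n₁n₂/12)[(N+1) − Σ(t³−t)/(N(N−1))] = 270.75 × (115 − 401184/12882) = 22704.
- z = (2801 − 3277.5)/√22704 = −3.16, so p=0.0016. Both medians are 0.
- Mean changes: −23/57 = −0.404 and −4/57 = −0.070. Difference: −19/57 = −0.33.
- Variances 0.3164 and 0.2807. SE = √[(0.3164+0.2807)/57] = 0.102. 95% CI: −0.333 ± 1.981×0.102 = −0.54 to −0.13.

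**Example 2: what stratifying does.** Assumed identical baselines, 28/20/8/1 per arm at scores 1/2/3/4. One-point improvements from scores 2, 3 and 4: adhesive 10+4+1, no adhesive 5+2+0. Nobody worsens.

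- Planned test: W−E = −228, V = 14549, z = −1.89, p=0.059.
- Van Elteren statistic: z = Σ[(W−E)/(N+1)] / √Σ[V/(N+1)²], summed over baseline strata.

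| Baseline | N | (W−E)/(N+1) | V/(N+1)² |
|---|---|---|---|
| 1 | 56 | 0 | 0 |
| 2 | 40 | −50/41 = −1.220 | 0.572 |
| 3 | 16 | −8/17 = −0.471 | 0.221 |
| 4 | 2 | −0.5/3 = −0.167 | 0.028 |
| Sum | 114 | −1.857 | 0.821 |

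- Four strata: z = −1.857/√0.821 = −2.05, p=0.040.
- Scores 3 and 4 pooled (N=18, terms −0.711 and 0.254): z = −1.930/√0.826 = −2.12, p=0.034.

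The 56 subjects at score 1 contribute nothing to the stratified test but add tied zeros to the planned one.

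**Power, by simulation.** All MSA distributions are assumed: 57 per arm, two-sided 5%, baseline mixes 50/35/13/2, 70/22/7/1, 35/45/17/3 and 10/60/25/5% at scores 1-4. Protocol 4.2 says an earlier index was "not sufficiently discriminatory enough for accurate evaluation of these subjects who mostly scored zero on this scale" and expects the MSA to be more sensitive, so baseline could sit mainly at 1 or at 2.

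- Latent bivariate normal cut at the mix, correlation 0.3 to 0.9, shift 0.5 SD: planned test about 28-92%, stratified about 50-95%, gain about 3 to 22 points.
- One-step transitions. Improvement among those at 2 or above: 20 vs 50%, 10 vs 35%, 30 vs 60% or 20 vs 65%. Worsening: 0, 5, 10 or 20%. With four mixes this makes 4×4×4 = 64 scenarios. Gain −0.5 to 16 points: at most 10 in 61 and at most 5 in 47. It is 0-3 with the 10/60/25/5 mix and 0-4 with 20% worsening.
- Type I error: 4.4-5.3% for both tests.

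**How often both medians are 0.** Take the 64 transition scenarios plus 40 latent-normal ones (4 mixes × 5 correlations × shifts of 0.5 and 1.0 SD). Both medians were 0 in more than half of trials in 86 of these 104. The exception matters: with 90% starting at 2 or above and 65% of them improving on adhesive, this happened in only 9-10% of trials.

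**The case against.** The other side has a good case, and much of it stands.

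- A rank test is a legitimate choice for a four-level ordinal score. A reader might infer that the planned test is biased or invalid. It is not: under randomization it holds its level, as the simulations confirm.
- A reader might infer that baseline MSA is ignored. The tested variable is change from baseline, so baseline is used; it is only not a covariate or stratum.
- The contrast with the questionnaires describes their planned models. If ANCOVA assumptions fail and no transformation works, SAP 4.4.2.1 falls back on a test such as Mann-Whitney, with no covariate or CI stated.
- Table 14.2.4.1 gives n, mean and SD of change by arm, so an unadjusted difference and CI can be rebuilt as in Example 1. The information is not lost; an adjusted, pre-specified presentation is.
- The SAP already goes beyond the protocol, which promised only an incidence summary.
- The power gain rests wholly on assumed distributions and can be nil.
- The SAP's display list is an attachment that cannot be read here. Its table shells may already contain a CI or a 1-4 frequency table, so nothing here shows that these are absent from the outputs.

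None of this supplies a baseline-adjusted between-arm estimate in the SAP text, and that gap does not depend on the simulations.

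**Conclusion.** The point holds as a modest improvement worth considering. On the SAP text, the MSA comparison neither adjusts for nor stratifies by baseline MSA, and it plans no between-group estimate or CI. This is certain from the wording.

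The size of the loss is less certain. Example 1 proves that p=0.0016 can stand beside two medians of 0. How often that would happen, and how much power stratifying would add, depend on an MSA distribution that the documents do not give. Under the stated assumptions the gain is about 3 to 22 points (latent-normal, 0.5 SD) or often 5 or fewer (one-step transitions). Example 2 should not be read as a rescued result: its p-values straddle 5% only because of the counts chosen.

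A reader might also infer that the trial's conclusion is at risk. It is not: success rests on Gum Comfort at Week 12, and the MSA is secondary, without a controlled testing level.

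**What to change.** In SAP 4.5.1.3, before unblinding:

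1. At each week, replace the unstratified test with a van Elteren test on MSA change, stratified by baseline MSA. Fix any pooling of scores 3 and 4 in advance. State that change is what is ranked: within an unpooled stratum this equals ranking the post-score, but within a pooled one it does not.
2. In Table 14.2.4.2, report one pre-specified baseline-adjusted between-group estimate with 95% CI, the same at every week. One option is the ANCOVA-adjusted mean difference with robust SE; its type I error in simulation was 3.9-4.7% (50/35/13/2 mix). The robust SE must be written in, because the questionnaire sections do not specify it. Do not switch effect measure on the observed data.
3. Word the hypothesis for the distribution of change instead of medians.

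A minor documentation point, subject to the unseen display list: show the 1-4 frequencies by arm and visit promised in Protocol 12.2.6, or record the change in SAP Table 5-1, which now has rows only for the per-protocol definition and Cronbach's alpha.

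The cost is SAP wording, a few lines of code, extra columns in one table and possibly one frequency table; no new data. There are downsides. Upper baseline strata will be sparse. The rank p-value and the CI come from different methods and may disagree. The estimate treats a four-level score as numeric. Under the transition assumptions, power gains little if few subjects start at score 1 or worsening is common.

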4.5.1.4 OHIP-Edent Questionnaire

This questionnaire comprises 19 questions grouped into 6 functional domains as provided in [Table 4-1](#). The questions have 5 possible responses ranging from 0 (Never) to 4 (Very Often) scale for all questions and thus a low score is more favorable and the overall score range is 0-76 where 0 is the best possible score.

Table 4-1 The Functional Domains of the OHIP-Edent Questionnaire

Domain	Questions	Score range
Functional limitations	1-3	0-12
Physical pain	4-7	0-16
Psychological discomfort	8-9	0-8
Physical disability	10-12	0-12
Psychological disability	13-14	0-8
Social disability	15-19	0-20

Summary tables of descriptive statistics (n, missing, mean, SD, SE, median, minimum and maximum) of the observed and change from baseline overall OHIP-Edent score will be presented ([Table 14.2.5.1](#)) at each week and for OHIP-Edent functional domain scores over time ([Table 14.2.5.3](#)) for subjects in the MITT population.

The change from baseline in overall OHIP-Edent score at Weeks 1, 4, 8 and 12 will be analyzed using ANCOVA with study product as a fixed effect and baseline overall OHIP-Edent score as a covariate. Adjusted means and their SEs, 95% CI, within treatment p-values for each product group will be displayed with product group difference, SE, 95% CI of the difference and the between-treatment p-value in ([Table 14.2.5.2](#)). All statistical tests of hypotheses will be two-sided and will employ a level of significance of $\alpha = 0.05$. Similar model will be used to analyze change from baseline OHIP-Edent functional domain scores at weeks 1, 4, 8 and 12 ([Table 14.2.5.4](#)).

As with the primary efficacy analysis, the model assumptions will be checked and suitable transformations or alternative non-parametric method will be performed if these are not met.

All OHIP-Edent responses for each question will be listed ([Listing 16.2.6.3](#)) by functional domain including the functional domain score, change from baseline domain score and overall OHIP-Edent observed and change from baseline values.

4.5.1.5 GOHAI Questionnaire

This questionnaire is comprised of 12 questions with 6 possible responses to each question (always, very often, often, sometimes, seldom and never). The responses are scored on a 0 (always) to 5 (never) scale for all questions except 3, 5 and 7 where the scoring is reversed, and thus the overall GOHAI scores can range from 0-60, where 60 is the best possible score.

The questions are grouped into 3 domains as detailed in [Table 4-2](#).

Table 4-2 The Functional Domains of the GOHAI Questionnaire

Table	Questions	Score range	Meaning
Functional	1-4	0-20	Subject's ability to eat, speak and swallow
Psychosocial	6,7,9-11	0-25	Subject's concerns, relationships and appearance
Pain/Discomfort	5,8,12	0-15	Subject's discomfort during chewing, sensitivity to hot/cold/sweets and use of medications to manage oral pain.

Summary tables of descriptive statistics (n, missing, mean, SD, SE, median, minimum and maximum) of the observed and change from baseline overall GOHAI score will be presented (Table 14.2.6.1) at each week for subjects in the MITT population.

The change from baseline in overall GOHAI score at Weeks 1, 4, 8 and 12 will be analyzed using ANCOVA with study product as a fixed effect and baseline overall GOHAI score as a covariate. Adjusted means and their SEs, 95% CI, within treatment p-values for each product group will be displayed with product group difference, SE, 95% CI of the difference and the between-treatment p-value in Table 14.2.6.2. All statistical tests of hypotheses will be two-sided and will employ a level of significance of $\alpha = 0.05$.

As with the primary efficacy analysis, the model assumptions will be checked and suitable transformations or alternative non-parametric method will be performed if these are not met.

A summary table for the GOHAI 3 functional domains will be presented individually and their respective questions (Table 14.2.6.3). Similar model used to analyze overall GOHAI score will be used to analyze the change from baseline GOHAI functional domain scores at weeks 1, 4, 8 and 12 (Table 14.2.6.4).

All GOHAI responses for each question will be listed (Listing 16.2.6.4) by functional domain including the functional domain score, change from baseline functional domain score and overall GOHAI observed and change from baseline scores.

